1.2 Secondary Objectives

Aim 2. To test whether 12 weeks of **TCC** compared to **HEW** training alter neural regulation of affect during an fMRI affect labeling task and functional connectivity in older adults with depressive symptoms. Imaging biomarkers will predict/moderate treatment response.

Hypothesis 2a: Compared to HEW, TCC will lead to improved functional connectivity in the Default Mode Network as measured with resting state (rs-) fMRI;

Hypothesis 2b: Compared to **HEW**, **TCC** will result in greater activation in the anterior cingulate;

Hypothesis 2c: Imaging biomarkers (hippocampal and anterior cingulate volume, white matter hyperintensity and DMN connectivity) will moderate and predict 1) rate of improvement in symptoms and function; and 2) improvement in cognitive performance.

Aim 3. To examine whether older depressed participants with MCI (LLD+MCI) differ in their cognitive trajectory and neural circuitry compared to older depressed participants without MCI (LLD-MCI) at extended follow-up of 6 and 12 months.

Hypothesis 3a: We hypothesize that changes in episodic memory and executive function will be greater in those with LLD+MCI than in those with LLD-MCI.

Hypothesis 3b: We hypothesize that changes in the default mode/hippocampal-frontal network and in the executive-control and cortico-limbic circuitry will be greater in those with LLD+MCI than in those with LLD-MCI.

Aim 4. *To examine whether greater degradation of neural circuitry is associated with greater cognitive decline.*

Hypothesis 4: We hypothesize that changes in default mode/hippocampal-frontal network and executive-control and cortico-limbic circuitry will be associated with decline in episodic memory and executive function.

Exploratory Aim 1: We will explore the role of treatment-resistance or poor response to the intervention in predicting cognitive outcomes.

Exploratory Aim 2: We will follow a subset of participants (those recruited within 2 years of the initial evaluation) to assess clinical trajectory of mood and cognitive symptoms with 24-month follow-up.

Exploratory aim 3: We will explore the difference in changes in gene expression and peripheral pro-inflammatory cytokines associated with clinical response to the interventions. To use peripheral blood to conduct transcriptome profiling with the same R01 protocols to identify gene expression and peripheral inflammatory biomarkers correlates of clinical response to TCC versus HEW.

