MRI Imaging Biomarkers: Imaging data will be acquired from 110 subjects (55 per group) at baseline, at 12-weeks post-randomization (or for early termination), and at 12-months post-randomization on a Siemens Prisma system using a 32-channel head coil. Each scanning session will last 60 minutes and include 1) a T1-weighted multi-echo MPRAGE (MEMPR) sequence with real time motion tracking and correction for the examination of brain structure; 2) a bandwidth matched T2-space sequence for detection and quantification of WMHs and CSF; and 3) three separate BOLD EPI sequences for the acquisition of rs- and task-related fMRI data used for the examination of emotional and working memory processing and functional connectivity. In addition, a 3-plane localizer and a non-BOLD EPI sequence co-planar to the fMRI data for cross-modal image registration will be acquired. The morphometry sequences are optimized for determining brain tissue contrast with reduced distortion.¹¹³

Table 5. fMRI sequences

3D T1 MEMPAGE	TEs/TR= 1.74, 3.6, 5.46, 7.32/2530 ms, TI=1260 ms, FA=7, FOV=256 mm, matrix=256x192, voxel size=1 mm ³ , run time: 8:14 min.
3D T2 SPACE	TE/TR= 425/3200 ms, FA='T2 var', FOV=256 mm, matrix=256x192, voxel size=1 mm ³ , ETL=769, 2xGRAPPA, run time: 4:43 min.
fMRI (emotion and working memory)	TE/TR=25/2500 ms, FA=80°, matrix 64x64, FOV=20 cm, 34 axial slices, slice thickness 3 mm, .75-mm gap, run time: ~6 min each.
Resting state fMRI	TE/TR=30/2000 ms, FA=80°, matrix 64x64, FOV=20 cm, 34 axial slices, slice thickness 3 mm, .75-mm gap, run time: 8 min.

Functional Imaging: To address our hypotheses that TCC versus HEW will result in greater activation in right VLPFC and the amygdala during emotional processing (Hypothesis 2a) and greater working memory-related activation in the DLPFC and other network regions (Hypothesis 2b) we will employ two widely-validated brain activation tasks that probe emotional processing and working memory function (see preliminary studies). Similarly, analysis of rs-fMRI data will

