9.2 Sample Size and Randomization

Power and sample size estimate: We assume that dropout will be at 10% and 20% at the end of 12 week treatment phase and 6 and 12 month follow-up, respectively. For Aim 1, if the treatment main effects are linear over the 12 week treatment phase on HAMD, our design with 7 time points (baseline, 2, 4, 6, 8, 10, 12 weeks) and with complete data on 99 subjects within each arm (10% dropout) will have 80% power at significance level $\alpha=0.05$ for detecting a treatment and time interaction corresponding to no difference at baseline and a difference of $d = 0.32$ SDs between any two arm at the end follow-up. Our R21 project found an effect size of 0.65 in HAMD between TCC and HEW at 12 weeks. If treatment effects continue to grow linearly over the 6 and

12 month follow-up, our design with complete data on 88 subjects within each arm (20% dropout) will have 80% power at significance level $\alpha=0.05$ for detecting a group difference between any two arms of $d = 0.36$ SDs at 6 and 12 month follow-up. The reported power is based on number of subjects with complete data, and hence is a conservative estimate of the actual power of our design, since the proposed GLMM framework utilizes all observed data collected from all subjects. In addition, the reported power analysis is based on a correlation of 0.5 between measurements obtained at different time points. Selection of the covariance structures within the GLMM model will be based on likelihood ratio test and/or AIC (Akaike Information Criterion). If we find either significant interactions or main effects, follow-up contrasts will be used to determine at which time points there has been significant change and/or differences in treatment effects relative to baseline.

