For Aim 2 of detecting group differences in imaging biomarkers, our design with complete data on 55 subjects within each arm at the end of treatment will have 80% power at significance level $\alpha=0.05$ for detecting a group difference between any two arms of $d = 0.53$ SDs. Our preliminary studies reported in Section 1.1.2 for antidepressant treatment response, found effect sizes of $d = 0.57$ for changes in BOLD response in bilateral occipital cortex and right VLPFC (faces affective reactivity task), in BOLD response in left DLPFC, premotor and bilateral posterior parietal regions (N-Back task) between baseline and end of treatment at 16 weeks. If TCC changes in brain function resemble those induced by psychopharmacological agents, our design will have enough power to detect group differences in imaging biomarkers.

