Exploratory Hypothesis 2c: Exploratory analysis: Exploratory variables will include hippocampal and anterior cingulate volume and white matter high intensity. To test hypotheses about the relationships between the imaging metrics and the primary outcomes in mood and cognition, we will derive domain summary scores for the 2 cognitive domains of interest, memory, and executive function. We will assess treatment moderator effects of baseline hippocampal and anterior cingulate volume and white matter high intensity on HAMD and memory and executive function domain scores. Statistical evaluation of moderators will be done by including the posited moderator variable as an independent variable and evaluating the moderator x treatment group interaction term in the GLMM models proposed in Aim 1. In addition we will assess the treatment mediator effects of change in DMN connectivity on change in HAMD and memory and executive function domain scores. Mediation effects will be assessed via multiple regression models, where the posited mediator variable is regressed on treatment, outcome is regressed on treatment and the outcome is regressed on the mediator and the treatment. For confirmation of the mediation effect, treatment effects need to be found significant on the outcome and the mediator as well as a decreased treatment effect size on the outcome in the presence of the mediator.

Exploratory aim 1: We will explore the difference in changes in gene expression and peripheral pro-inflammatory cytokines associated with clinical response to the interventions, by comparing the change in these markers between the two intervention groups and by examining how the change in these markers correlate with changes in depression and cognitive scores in the two groups.

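### The exploratory mediation rule counts any drop in the treatment effect as confirmation, so a DMN mediator unrelated to outcome meets that condition about half the time once both treatment effects are significant

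*Combined protocol and SAP*

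**What the plan says.** Under Exploratory Hypothesis 2c, section 9.6 plans to "assess the treatment mediator effects of change in DMN connectivity on change in HAMD and memory and executive function domain scores". It names three regressions: mediator on treatment, outcome on treatment, and a third in which "the outcome is regressed on the mediator and the treatment". The requirement for confirming mediation is "treatment effects need to be found significant on the outcome and the mediator as well as a decreased treatment effect size on the outcome" when the mediator is included.

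That gives three conditions: (i) treatment significant on the outcome, (ii) treatment significant on the mediator, and (iii) a smaller treatment effect after adjustment. Conditions (i) and (ii) are significance tests. Condition (iii) has no test, interval or minimum reduction.

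Section 1.2 has related hypotheses. Hypothesis 2c says that imaging biomarkers, DMN connectivity among them, will moderate and predict improvement in symptoms, function and cognition. Hypothesis 4 says that "changes in default mode/hippocampal-frontal network and executive-control and cortico-limbic circuitry will be associated with decline in episodic memory and executive function". Neither adds a test to the mediation rule.

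Section 9.6 does not say which subjects enter each regression, or on what scale the effect size is compared. The sample matters because section 6.2.1 states: "Imaging data will be acquired from 110 subjects (55 per group) at baseline", which is half of the 220 randomised.

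**The concern.** Mediation needs two links: treatment to mediator, and mediator to outcome given treatment. Condition (ii) tests the first. Nothing tests the second, although the third regression estimates it. If TCC improves mood and also changes DMN connectivity, conditions (i) and (ii) will tend to be met whether or not the two changes are connected. The claim then rests on condition (iii) alone.

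At stake is the only planned analysis of whether DMN change carries the TCC effect on mood and cognition. If condition (iii) can be met by chance, a report of confirmed mediation says little about that link.

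**Working it through.** **The plan's own figure.** The documents give no error rate or power for the mediation rule. The nearest figure is Aim 2 in section 9.2: 80% power at d = 0.53 with 55 per arm and α = 0.05 (sidedness not stated, taken as two-sided). Φ(0.53 × √(55/2) − 1.96) = Φ(0.819) = 79.4%, so it reproduces.

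**The identity.** Let â be the treatment effect on the mediator, b̂ the treatment-adjusted mediator coefficient, ĉ the total effect and ĉ′ the adjusted effect. In least squares with the same subjects, the same covariates and unstandardised coefficients, ĉ − ĉ′ = â × b̂. If the true b is 0 and there is no residual correlation, the sign of b̂ is chance. Condition (iii) then holds with probability about 1/2, whatever the sample size or effect size.

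**Inputs for the simulation.**
- n = 55 per arm as planned, and 50 per arm (55 less 10% dropout, rounded).
- Outcome effect 0.65 SD, from section 9.2: "Our R21 project found an effect size of 0.65 in HAMD between TCC and HEW at 12 weeks".
- Mediator effect 0.57 SD. Section 9.2 reports this "for changes in BOLD response in bilateral occipital cortex and right VLPFC" and other regions. It is an antidepressant result, worded as a change from baseline to week 16, so here it is only an assumed between-arm DMN effect.
- Unit variances, and zero residual correlation for the inert mediator.

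**Inert mediator, given (i) and (ii)** (200,000 trials). Condition (iii) is met in 49.8% (50 per arm) and 50.2% (55 per arm). The median spurious drop is 6.2% and 5.9%. A separate run over other effect sizes, at 49 and 55 per arm, gave 49.5-50.3% wherever treatment moved the mediator.

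**The unstated choices do not rescue the rule.** Standardising by residual SD gives 52.1% and 52.4%. Taking the total effect from all HAMD subjects (99 or 110 per arm) and the adjusted effect from the scanned subjects gives 49.9% and 50.1%. That second choice also lowers confirmation of a real link of 0.2-0.3, given (i) and (ii), from 98-99.9% to 78-89%.

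**Overall false confirmation.** For an inert mediator this is about P(i) × P(ii) × 0.5. At 55 per arm with 0.57 and 0.65 SD: P(ii) ≈ Φ(0.57 × 5.244 − 1.96) = 0.848, P(i) ≈ Φ(0.65 × 5.244 − 1.96) = 0.926, and 0.848 × 0.926 × 0.5 = 39.3%. Simulated rates:

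| Mediator effect, HAMD effect (SD) | 50 per arm | 55 per arm |
|---|---|---|
| 0.57, 0.65 | 36.0% | 39.0% |
| 0.30, 0.65 | 14.2% | 15.8% |
| 0.57, 0.32 | 14.2% | 16.3% |
| 0.30, 0.32 | 5.6% | 6.6% |
| 0, 0.65 | 2.2% | 2.4% |

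The 0.32 is the detectable HAMD difference in section 9.2. The 0.30 is an assumption.

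**With a test of the missing link added.** Requiring a 95% bootstrap interval for the indirect effect to exclude zero in the reducing direction (8,000 trials) leaves 129 of 5,784 = 2.2% (50 per arm) and 174 of 6,172 = 2.8% (55 per arm), given (i) and (ii). A two-sided 0.05 test of b̂ in the reducing direction gives 2.3-2.6% at 55 per arm. Direction must be kept: at 50 per arm, 130 of the 259 intervals excluding zero pointed to a larger treatment effect.

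**Power for a real link**, overall confirmation as counts out of 8,000, current rule → with the bootstrap condition:

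| b | 50 per arm | 55 per arm |
|---|---|---|
| 0.4 | 5,978 → 5,836 (74.7% → 73.0%) | 6,370 → 6,281 (79.6% → 78.5%) |
| 0.3 | 5,902 → 4,968 (73.8% → 62.1%) | 6,280 → 5,527 (78.5% → 69.1%) |
| 0.2 | 5,763 → 2,892 (72.0% → 36.2%) | 6,172 → 3,350 (77.2% → 41.9%) |

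**The case against.** **The conditions may be necessary, not sufficient.** The text lists what is needed and does not say that any drop suffices. A reader shown a 6% drop would see how small it is. This does not rescue the rule: no further criterion is given, so a 6% drop meets everything written.

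**The analysis is exploratory.** This stands and limits the weight of the point. Section 1.2 speaks of moderating and predicting; mediation enters only in section 9.6, under an exploratory label. That section still sets a rule for confirmation, so the rule should be able to support one.

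**The imaging-outcome relation is addressed elsewhere.** A reader might infer that the plan never considers it. Hypotheses 2c and 4 do pose such associations. For Hypothesis 4 no method is given, so whether treatment would be adjusted for is unknown. Neither hypothesis enters the mediation rule.

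**The high overall rates use favourable effects.** This stands. The 36-39% needs both assumed effects, and the 0.57 is a poor proxy for a between-arm DMN effect. The conditional 50% does not depend on either value.

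**The fix is partial and costs power.** This also stands. In the model used, a residual correlation of 0.3 from confounding gives the same data as a real link of 0.3, so it would still be confirmed in 62-69% of trials after the fix. The power lost at weak links is power that the current rule has only because it omits a test.

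**Conclusion.** The point holds for the mediator-outcome link. Once both treatment effects are significant, condition (iii) confirms about 50% of inert mediators against about 98% or more of real ones with a link of 0.2-0.3, a factor of about 2. This assumes least squares on common subjects and covariates, unstandardised effects and no residual correlation. The alternative samples and scale that were checked leave the inert rate at 50-52%.

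Two stronger readings are not supported. One is that the rule has a 50% false-positive rate overall: the two significance conditions also apply, and the overall rate runs from about 2% to 39% over the effects examined. The other is that a confirmed result carries no evidence at all. Against a mediator that treatment does not move, the rule confirms about 2%, compared with 74-79% for a real link of 0.3. The HAMD primary analysis and the co-primary imaging analyses do not use this rule and are unaffected.

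**What to change.** Revise the mediation paragraph in section 9.6 as follows:

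- Keep the decreased-effect condition, which supplies direction.
- Add that either the indirect effect (95% bootstrap interval) or the treatment-adjusted mediator coefficient (two-sided 0.05) must differ from zero in the direction that reduces the treatment effect. The coefficient test is the simpler option and controls the inert rate about as well.
- Fit all three regressions on the same scanned subjects with the same covariates, and compare unstandardised coefficients.
- State that the claim assumes no unmeasured mediator-outcome confounding, which this test does not remove.

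The cost is one paragraph and a small analysis of data already planned. Apparent power with the bootstrap condition falls by about 1-2 points at b = 0.4, 9-12 at b = 0.3 and 35-36 at b = 0.2. No primary or co-primary analysis changes.

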9.7 Data Sharing & Future Research

Data from this study will be used for other ongoing or future research projects in the following ways:

- Share it with researchers in the U.S. or other countries for data analyses
- Use it to improve future protocol
- May be shared with the Sponsor

10. DATA COLLECTION AND QUALITY ASSURANCE

10.1 Data Collection Forms

A blinded observer will perform outcome assessments. All key personnel involved in any aspect of data access and query must complete training on HIPAA and other good research practice modules as required by UCLA. Backup files archived on removable media and paper forms are stored in locked cabinets accessible only by appropriate personnel. We maintain confidentiality of all research subjects and follow the guidelines of the UCLA OPRS.

We will maintain the subjects' privacy in our data collection methods. The interviews will be conducted in a private interview room where conversations cannot be overheard by others in the Semel Institute building. All medical procedures, including fMRI will be conducted in a private examination room at the UCLA Semel Institute, CTRC and MPTF outpatient facilities, or the Brain Mapping Center.

The risk of breach of confidentiality is reduced by: 1) storing records in a locked file, with access available only to the PI and designated project staff; 2) removing identifying information from all data during the data analysis phase of the project; and 3) removing identifying information from all data presented publicly in lectures, seminars, or publications.

The Data Collections Forms are described in Appendix B: Table 3. Assessment Schedule. Additional NCCIH forms are listed below:

1. Visit Checklist
2. Documenting the Consent Process
3. Inclusion/Exclusion Core Form
4. Demographics Form
5. Medical History Form
6. Vital Signs
7. Physical Exam
8. Randomization and Enrollment Form
9. Concomitant Medication Form

10.2 Data Management

Data management: Data management and statistical support for this project, other than storage and processing of raw imaging files, will be provided by SIStat, the biostatistics core in UCLA's Semel Institute for Neuroscience and Human Behavior, (project co-investigator, [name]). [name] will collaborate with [name] on data analysis. SIStat staff will construct a secure customized web-based data collection and management system for this study incorporating the

subject registry, administrative tools and protocols, and a centralized database which will accommodate both direct data entry and electronic upload of summary files. The fMRI data will be stored in the computing cluster in the UCLA Brain Mapping Center (see Facilities) and processed by members of the [name]/ [name] labs, who have specific expertise in the study paradigms; the resulting derived measures will be uploaded to the centralized database. Moreover, access to the data system, including the randomization program, is controlled via a hierarchical system of password protected logins, ensuring that study personnel can view only the parts of the system that are appropriate for their role. This helps to maintain blinding and ensure subject confidentiality. Careful security protocols will also be maintained prior to the entry of data into the online system. Specifically, paper copies of patient study forms will be stored in locked file cabinets and will be accessible only to authorized personnel. A shredder will be used to discard all unwanted study documents.

10.3 Quality Assurance

10.3.1a. Training in assessments

SOP: Clinical Assessments. All behavioral outcome assessments will be identical in all groups and performed by the trained raters blind to the treatment assignment. Inter-rater reliability for all instruments will be established at the beginning of the trial. All research associates will be trained by the PI, [name], and [name] on administration of all clinical study assessment including DSM-5R SCID interview. Inter-rater reliability will be established on all assessment instruments on the first 5 recruited subjects and rechecked every year for reliability to maintain reliability index high.

Neuropsychological Assessment. Psychometrists in the study will be taught how to administer the test battery by [name] or a designated post-doctoral geriatric neuropsychology fellow under [name] supervision. The psychometrist will be observed in testing and scoring, and the work product will be reviewed. Each psychometrist is given feedback on areas of strengths and weaknesses, and a final overall rating as to readiness to start testing subjects.

10.3.1b. Training in administering interventions.

SOP:

Health and wellness education (HEW). [name] and trained study staff at both sites will implement HEW using a manual that will present educational information and describe learning objectives and patient activities to promote integration of material. The detailed protocol for Health Education has been developed and used in the pilot project. The HEW sessions will be held once a week for 60 minutes over the 12-week treatment period. We will follow a didactic format, inviting experts to lecture on key topics, followed by focused group discussion, and post-discussion self-help quizzes to assess patient learning.

SOP: [name] will provide weekly supervision for health education instructors to monitor consistency and adherence to the educational protocol.

Fidelity of Training: Our group will take the following steps to facilitate and ensure the fidelity of training. For the HEW condition, the co-investigator ([name]) meets with staff to learn the HEW training manual. During this meeting, the group will go over the material. Standard background readings are assigned to trainers on each topic in the training manual. Standard Readings on weekly HEW topics assigned for each session to teachers. Trainers receive education on other factors important to instilling belief in the effectiveness of the HEW training in subjects, including:

- How to develop rapport
- Using an effective presentation style (speech rate, volume, eye contact, how to facilitate subject participation in the groups)

- Addressing subjects' expectations for benefit—educating subjects so that they develop realistic expectations about how HEW condition can be beneficial.

Adherence and Quality control: After the training meeting, [name] will implement quality control assessment to determine each trainers' readiness for implementation of HEW. This will include mock presentations of the material on which trainers present to each other, and [name], and are then rated (pass, needs improvement, and comments) on several dimensions including the material in the manual as well as the quality of presentation style. Presenters are given positive feedback and constructive criticism on their presentation. If trainers do not meet the 'pass' standard, will be given more time to practice and learn the material and will be re-reviewed. Finally, trainers will receive weekly supervision by [name] used to monitor trainers' adherence to the intervention and protocol.

Tai Chi Chih. The Tai Chi Chih instructors will follow the same manual for this interventions. All instructors have been trained and certified by the Tai Chi Chih Association and its founder [name]. We will contact Tai Chi Chih Association to send monitors or provide other ways of monitoring the TCC instructor's adherence to the manual protocol.

